SNRI	Serotonin –Norepinephrine Reuptake Inhibitor
SOC	System Organ Class
SSRI	Serotonin-Specific Reuptake Inhibitor
WBC	White Blood Cell
WHO	World Health Organization

PROTOCOL SYNOPSIS

A Multicentre, Long-term Safety, Efficacy and Pharmacokinetics Study of Lubiprostone in Paediatric Subjects Aged ≥6 to <18 years with Functional Constipation		
Study Phase	Phase 3	
Short Title	Long-term safety extension study of lubiprostone for the treatment of paediatric functional constipation in subjects aged ≥6 to <18 years	
Objectives, Study Medication and Dose Regimen:	
To assess the long-term safety, efficacy, and pharmacokinetics of oral lubiprostone 12 or 24 mcg capsules dosed twice daily (BID) when administered orally for 36 weeks in paediatric subjects with functional constipation. Evaluation of lubiprostone safety is the primary objective in this study.
 
Dose assignment will be based on the dose they were receiving at the time of rolling over from the preceding, double-blind study (SAG/0211PFC-1131) into this safety extension study for those subjects who were randomised to receive lubiprostone during the preceding study. For subjects who received placebo during the preceding study, assignment of dose will be assigned based on subject body weight at the time of rollover to this extension study. All dose assignment will be handled by an Interactive Voice/Web Response system (IXRS) and will continue to maintain blinding with respect to the treatment assignment in the preceding trial.
	
Assumed No. of Sites:	Approximately 130 (Northern America and Europe)	
Est. No. Enrolled Subjects:	415 subjects who completed Study SAG/0211PFC-1131	
Est. No. Screened Subjects:	NA	
Duration of Participation:	Up to 42 weeks (including follow-up)	
Duration of Treatment:	36 weeks	
Study Schedule:	Visit 9: Enrolment (Clinic Visit)	Day 1 (coincides with SAG/0211PFC-1131 study Visit 7)
	Visit 10: Interim Treatment Visit (Clinic Visit)	Week 1 Visit (±2 days)
	Visit 11: Telephone Assessment	Week 4 Visit (±3 days); Month 1
	Visit 12: Interim Treatment Visit (Clinic Visit)	Week 12 Visit (±3 days); Month 3
	Visit 13: Telephone Assessment	Week 16 Visit (±3 days); Month 4
	Visit 14: Interim Treatment Visit (Clinic Visit)	Week 24 Visit (±3 days); Month 6
	Visit 15: Telephone Assessment	Week 28 Visit (±3 days); Month 7
	Visit 16: End-of-Treatment (Clinic Visit)	Week 36 Visit (+3 days); Month 9
	Visit 17: Follow-Up (Clinic Visit)	Week 40 Visit (+3 days); Month 10

Inclusion Criteria:	
 1. Written informed consent obtained from subject and/or parent/legal guardian (and assent from subject where applicable). 2. Subject must have completed the entire 12-week treatment period from the preceding study (SAG/0211PFC-1131) prior to enrolment. 3. Subject must continue to abstain from taking concomitant medication (prescribed or over-the-counter) that affects gastrointestinal motility; these medications include: 
 a. Cholinesterase inhibitors; anti-spasmodic, anti-diarrheal, anti-constipation, or prokinetic agents; laxative agents (e.g., PEG 3350), including homeopathic remedies; b. Tricyclic antidepressants; or c. Any medication, at the discretion of the Investigator, known to relieve or cause constipation or constipation-related symptoms, and which the Investigator, based on the medical history of the subject, suspects to be a contributing factor to the patient's chronic constipation, or may otherwise confound the evaluation of treatment response. 
Exceptions: Treatment with anticholinergic agents, SSRIs, SNRIs, or MAO inhibitors is allowed if a stable dose has been used for at least 30 days prior to the Baseline Visit (of the preceding study SAG/0211PFC-1131) and not likely to change during the study.
 4. Subject (and if necessary, parent/legal guardian) must be willing and able to use or administer recommended (rectal and/or oral) rescue medications if needed. 5. If subject is taking a fibre supplement (e.g., Metamucil®, PerDiem®, Fybogel), usage must have been at a stable dose not likely to change during the study. 6. Subject and his/her parent/legal guardian must be willing and able to fill out his/her own diary.
Exclusion Criteria:	
 1. Subject has current evidence of untreated faecal impaction. 2. Subject has experienced an adverse event during the SAG/0211PFC-1131 study which the Investigator considers to be clinically significant and would limit the subject's ability to participate in the trial. 3. Subject has had a significant change in their medical status, newly diagnosed and uncontrolled cardiovascular, liver or lung disease, neurologic or psychiatric disorder, or other systemic disease, which the Investigator considers to be clinically significant and would limit the subject's ability to participate in the trial. 4. Subject has developed abnormal laboratory test (haematology, urinalysis, or blood chemistry), which in the Investigator's opinion is clinically significant, unexplained, and would limit the subject's ability to participate in the trial. 5. Subject (female of childbearing potential) has a positive pregnancy test, refuses/unwilling to undergo pregnancy testing, and/or does not agree to use protocol-specified contraceptive measures for the duration of the study. 6. Subject demonstrated non-compliance with study protocol (i.e., dosing schedule, visit schedule, diary completion, or study procedures) during the SAG/0211PFC-1131 study.
Rescue Treatment	
In the event that no bowel movement (BM) has occurred within a 3-day period, the use of recommended rescue medications may be allowed per Investigator's instructions. Recommended rescue medications include bisacodyl, senna, sodium picosulfate, and saline enemas.


Safety Endpoints:
	
The safety endpoints are as follows:
 
 • Incidence of adverse events (AEs) grouped by MedDRA System Organ Class (SOC) and Preferred Term • Changes from baseline in clinical laboratory parameters (haematology, serum chemistry, urinalysis) • Changes from baseline in physical examination • Changes from baseline in vital sign measurements, including height and weight 
 ○ Height will be measured using a wall-mounted stadiometer, if available • For those subjects who were aged 6 to 9 or 14 to 17 at the time of enrolment into the SAG/0211PFC-1131 study, and who were qualified to participate and enrolled in the dual-energy X-ray absorptiometry (DXA) substudy: 
 ○ Percent changes from baseline in bone mineral density (BMD) and bone mineral content (BMC) ○ Changes from baseline in BMD Z-scores and in height-adjusted Z-scores, as assessed by DXA for DXA Subgroup ○ Changes from baseline in height and weight Z-scores for DXA Subgroup ○ Incidence of clinical fractures 
A Data Safety Monitoring Board (DSMB) will monitor safety data on a regular basis throughout the study. Specifics, including meeting frequency and stoppage criteria, are provided in the DSMB Charter.


Efficacy Endpoints:
	
The efficacy endpoints are as follows:
 
 • Overall and monthly changes from baseline in BM and SBM frequency rate • Overall and monthly assessments of the average degree of, and changes from baseline in: 
 ○ Stool consistency of SBMs ○ Straining associated with SBMs ○ Abdominal pain associated with SBMs ○ Constipation severity • Monthly SBM Response 
 ○ A monthly responder is defined as a subject who is a weekly responder for 3 of 4 weeks per month. ○ A weekly responder is defined as a subject who has a frequency rate of ≥ 3 SBMs/week and an increase from baseline of ≥ 1 SBM/week for that week. • Overall and monthly assessment of average treatment effectiveness rating • Overall Health-related quality of life (PedsQL™) • Overall and monthly change from baseline in incontinence episodes frequency (analysis performed for subset of subjects presenting with incontinence at baseline) • Overall and monthly change from baseline in the production of large diameter stool (a stool that clogs the toilet) frequency • Overall and monthly change from baseline in frequency of faecal impaction • Overall and monthly change from baseline in proportion of BMs and SBMs in toilet overall • Overall and monthly change from baseline in frequency of retentive posturing or excessive volitional stool retention

Pharmacokinetic Evaluation:	
Plasma samples will be collected for population pharmacokinetic (PK) modeling at Visit 9 as follows:
 
 • Pre-dose and 1 sample between 30 and 90 minutes after dose administration (2 samples total) 
A population PK analysis will be performed using the concentration-time data from the sparse PK samples in this study. The analysis may include data from other studies with lubiprostone in adults, paediatric subjects, or healthy volunteers. A separate analysis plan for the population PK analysis will be prepared prior to database lock.

Sample Size Estimate Calculation	
For purposes of establishing the safety profile with lubiprostone long-term exposure in paediatric functional constipation, safety data from subjects enrolled in this study will be considered together with the 100 subjects enrolled in Sucampo study SAG/0211PFC-11S2 (subjects in this study will be below 6 years old).
 
The sample size is based on the expected attrition that would occur and the remaining number of safety evaluable subjects at each timeframe during the study.

Statistical Methodology	
Efficacy analysis will be based on modified intent-to-treat (mITT) population which includes all enrolled subjects who take at least one dose of study medication and have at least one treatment period diary entry. Categorical and discrete variables will be summarized by counts and percentage, and continuous variables will be summarized by descriptive statistics. Detailed statistical methodology will be documented in the Statistical Analysis Plan (SAP).
 
Adverse events will be summarized in terms of incidence by treatment group and overall. Changes from baseline or clinical abnormalities in clinical laboratory data, physical examinations, and vital signs will be summarized by treatment group and overall.
 
The PK profile for lubiprostone will be determined from the concentration-time data for all evaluable subjects based on the plasma concentrations lubiprostone (if measurable) and of lubiprostone's metabolite, M3. Actual post-dose sampling times relative to time of study medication administration, rather than scheduled sampling times, will be used in all PK profile computations involving sampling times.

SCHEDULE OF EVALUATIONS

Study Week(s) / Month(s)	0	1 / 0	4 / 1	12 / 3	16 / 4	24 / 6	28 / 7	36 / 9	40 / 10
Study Day(s)	1	8 (± 2)	29 (± 3)	85 (± 3)	113 (± 3)	169 (± 3)	197 (± 3)	253 (+ 3)	281 (+ 3)
Visit Number	9	10	11	12	13	14	15	16	17
Visit Type	Enrolment ¹	Clinic Examination	Telephone Assessment	Clinic Examination	Telephone Assessment	Clinic Examination	Telephone Assessment	End-of-Treatment Clinic Examination	Follow-up Clinic Examination
Assessment									
Informed Consent/Assent	X								
Inclusion/Exclusion Criteria Review	X								
Demographics	(V1)								
Medical History	(V1/V2)								
Vital Signs, Height, and Weight ²	(V7)	X		X		X		X	X
Physical Examination ³	(V7)	X		X		X		X	X
Pharmacokinetic Sampling ⁴	X								
Blood Chemistry, Hematology, Urinalysis	(V7)	X		X		X		X	X
Pregnancy Test ⁵	(V7)	X		X		X		X	X
Concomitant Medications									
Adverse Events									
BMD and BMC Assessments ⁶	(V7)							X	
Study Medication Distribution ⁷	X	X		X		X			
QoL Assessment	(V7)			X		X		X	
Study Treatment									
Study Medication Collection		X		X		X		X	
Electronic Diary ⁸									

Note: The Visit numbers in parentheses are in reference to the preceding placebo-controlled study (SAG/0211PFC-1131).

¹ The End-of-Treatment Visit (V7) in study SAG/0211PFC-1131 will serve as the Enrolment Visit and the corresponding assessments are designated above as "V7". Other corresponding visits from preceding study are also designated by the visit number;

² Measure predose vital signs at Visit 9, as well as measurement of heart rate and blood pressure 1 hour after the first dose of study medication. If blood pressure and/or heart rate are, according to the Investigator, clinically significantly elevated relative to predose at the 1 hour postdose measurement, additional measurements should be taken again at 2 hours and 3 hours postdose. Subjects should be asked to remain seated for at least 5 minutes prior to measurement of vital sign parameters. A wall-mounted stadiometer, where available, should be used for measurement of height. Vital sign assessments will be performed prior to PK sampling when these assessments are collected at the same visit. Record the time of all vital sign measurements in the source documents. Age-appropriate equipment, e.g., blood pressure cuffs, should be used for all assessments;

³ Complete comprehensive physical examinations at Enrolment and End-of-Treatment visits. An abbreviated physical examination is to be performed at all other visits;

⁴ PK samples will be collected predose and 1 sample between 30 and 90 minutes after dose administration (2 samples total). PK samples will be taken under non-fasting conditions. The samples will be collected via direct venipuncture. Approximately 8 mL of blood will be taken for each sample such that the total of all PK samples does not exceed 50 mL or 5 mL/kg of body weight;

⁵ Urine pregnancy tests will be performed at all study visits on subjects of childbearing potential.

⁶ All subjects who withdraw from the study after Visit 12 (Month 3) should complete the final visit of the treatment period (Visit 16) and therefore have a final DXA assessment performed. This will only be required for subjects that were originally part of the DXA subgroup. Any subject demonstrating a decline in 4% in BMD at any skeletal site from Screening to End of Treatment should additionally undergo a follow-up DXA assessment 6 to 12 months later;

⁷ Observe the subject or parent/legal guardian as he/she administers the first dose of study medication while in the clinic at Visit 9. Over the next 1 hour, monitor subject for any adverse reactions. One bottle of study medication will be provided at Visit 9 and then 3 bottles each at Visits 10, 12 and 14. Subjects should return the used bottle of study medication at each clinic visit for collection by site for drug accountability. If the study medication is not returned, the bottle of all unused study medication should be returned to the site at the subsequent office visit. The subject will be instructed to take the study medication only from the newly dispensed bottle;

⁸ Change eDiary mode to new treatment mode (associated with current study - SAG/0211PFC-11S1) at Visit 9.

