6.1.2 Enrolment Period – Visit 9 (Study Day 1)

At this visit, a review of the inclusion and exclusion criteria will be conducted for all subjects to ensure the subject remains eligible for the study. Consent/assent must be obtained before any study procedures are performed.

Note: This visit will coincide with Visit 7 from the preceding study (SAG/0211PFC-1131). The following procedures that are recorded as part of Visit 7 from SAG/0211PFC-1131 will also be recorded to this visit and therefore do not need to be repeated:

- Completion of PedsQL™ questionnaire by subject or parent/legal guardian prior to conducting other visit procedures;
- Measure predose vital signs, including height and weight; measure heart rate and blood pressure 1 hour after the first dose of study medication. Subjects should be asked to remain seated for at least 5 minutes prior to measurement of vital sign parameters. If blood pressure and/or heart rate are confirmed to be clinically significantly changed (as defined in [Section 6.3](#)) at the 1 hour postdose measurement relative to predose, additional measurements should be taken again at 2 hours and 3 hours postdose. Record the time of vital sign measurements in the source documents. A wall-mounted stadiometer, where available, should be used for measurement of height. Age-appropriate equipment, e.g., blood pressure cuffs, should be used for all assessments;
- Collect blood and urine samples for clinical laboratory analysis. A total of about 5.5 mL of blood will be collected for clinical laboratory analysis;
- Perform a full physical examination;
- Measurement of BMD and BMC via DXA of lumbar spine and total body (less head), if available, for DXA Subgroup (Subjects 6 to 9 and 14 to 17 years of age). This will only be required for subjects that were originally part of the DXA subgroup; and
- Urine Pregnancy Test – All female subjects of childbearing potential will have a urine dipstick pregnancy test to determine their pregnancy status prior to the dispensing of study medication.

As part of this visit, the following procedures will take place:

- Update medical history. Any new medical information should be added to the subject's baseline history (AEs will be captured on the AE page);

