6.3 Safety Evaluations

The following safety evaluations will be performed during the study to measure the safety of the study medication:

Adverse Events: AEs will be reported by the subject from the time of informed consent through the end of the follow-up period. AEs will be followed by the Investigator as determined by Sponsor or designee. Further details on AE reporting are provided in [Section 7](#). Any study medication related AEs persisting at the end of the study will be followed until resolution, or until a clinically stable endpoint has been reached.

In this study, faecal impaction and bone fractures will be captured as AEs. The events of faecal impaction will be used for the analysis of the fecal impaction frequency during the study (see [Section 8.6.2.5](#)).

Clinical Laboratory Tests: The following laboratory tests will be conducted and the appropriate Investigator shall determine the clinical significance of any out-of-range values.

- **Hematology Panel:** Hemoglobin, hematocrit, MCV, MCH, MCHC, RBC, WBC, white blood cell with absolute counts and percent differentials (neutrophils, lymphocytes, monocytes, eosinophils, basophils), platelet count.
- **Chemistry Panel:** Total cholesterol, triglycerides, glucose, total protein, albumin, alkaline phosphatase, AST, ALT, GGT, iron, LDH, total bilirubin, direct bilirubin, BUN, uric acid, creatinine, sodium, potassium, chloride, bicarbonate, calcium, phosphorus, magnesium.
- **Urinalysis:** Protein, glucose, ketones, occult blood, pH, specific gravity, color, appearance, leukocyte esterase, nitrite, bilirubin, and macroscopic examination. Microscopic examination will be done if abnormalities are present. Urine samples will be collected, when possible.

Physical Examination: Physical examinations will be conducted at various timepoints during the study. Any new post treatment findings or changes, as noted by the Investigator, will be reported as an AE.

Vital Signs:

Vital signs (including height and weight at designated visits) will be recorded during the study. Any post treatment clinically significant changes in vital signs (including weight) shall be noted by the Investigator and reported as an AE. Additional guidance regarding assessment of changes in blood pressure and heart rate are provided below.

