Normal blood pressure ranges will be based on the National Institutes of Health National Heart, Lung, and Blood Institute chart ([Appendix 2](#)). If, at 1 hour postdose, a change in blood pressure of greater than 15 mmHg from the predose assessment is observed, and this change is confirmed by a repeat measure, additional measurements must be taken at 2 and 3 hours postdose. If the observed change is sustained through the three post-dose measurements, it should be considered a clinically significant change, which must be reported as an adverse event.

Normal heart rate ranges will be based on the Silverman pediatric ranges ([Appendix 3](#)). If, at 1 hour postdose, a change in heart rate of greater than 20 beats per minute (bpm) from the predose assessment is observed, and this change is confirmed by a repeat measurement, additional measurements must be taken at 2 and 3 hours postdose. If the observed change is sustained through the three post-dose measurements, it should be considered a clinically significant change, which must be reported as an adverse event.

Rescue Medication Usage: All medications used emergently by the subject to relieve constipation, will be captured during their participation in the study.

Bone Growth Assessments: BMD and BMC assessments will be performed during the study for those subjects enrolled in DXA Subgroup only.

Any subject demonstrating a decline in 4% in BMD at any skeletal site from Screening to End of Treatment should additionally undergo a follow-up DXA assessment 6 to 12 months later.

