7.2.5 Vital Signs

A change in the value of a vital sign measurement can represent an AE, as discussed in Section 6.3 for blood pressure and heart rate. The Investigator should decide, based on the criteria in Section 6.3, or per their discretion (for other vital sign measurements), and the clinical condition of a subject, whether a change in vital signs is clinically significant and therefore represents an AE.

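### Schedule footnote 2 calls for the 2 h and 3 h blood pressure and heart rate readings only after rises the Investigator judges significant, against the numeric trigger for any change in Section 6.3

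*Combined protocol and SAP*

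**What the plan says.** The protocol states the Visit 9 rule for extra post-dose readings in three places and relies on it in a fourth.

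- **Schedule of Evaluations, footnote 2.** The condition is "If blood pressure and/or heart rate are, according to the Investigator, clinically significantly elevated relative to predose at the 1 hour postdose measurement"; readings at 2 and 3 hours should then follow. The footnote gives no number and no confirming repeat.
- **Section 6.3, Vital Signs.** The blood pressure trigger reads: "If, at 1 hour postdose, a change in blood pressure of greater than 15 mmHg from the predose assessment is observed". Once a second reading bears this out, the 2 h and 3 h readings are mandatory. For heart rate the same structure applies to "a change in heart rate of greater than 20 beats per minute (bpm) from the predose assessment is observed". The later readings then settle the adverse event question: "If the observed change is sustained through the three post-dose measurements, it should be considered a clinically significant change". Reporting it as an adverse event is then compulsory.
- **Section 6.1.2 (Visit 9).** The condition is that blood pressure or heart rate is "confirmed to be clinically significantly changed (as defined in", with Section 6.3 named as the source of the definition. The word is changed, not elevated.
- **Section 7.2.5.** The Investigator's adverse event decision on vital signs is "based on the criteria in Section 6.3, or per their discretion (for other vital sign measurements". Blood pressure and heart rate are thus tied to Section 6.3, and discretion is left for the rest.

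**The concern.** Footnote 2 differs from Section 6.3 on three points of substance: direction (rises against any change), who decides (the Investigator against a threshold), and confirmation (none against a repeat reading).

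Safety is the primary objective, and change in vital signs is a listed safety endpoint. Visit 9 is the only visit with scheduled post-dose readings. For children who had placebo in the preceding study, it is also their first study dose of lubiprostone. The sustained-change rule in Section 6.3 needs readings at 1, 2 and 3 hours. Planned observation for adverse reactions after the dose lasts 1 hour, so a child for whom the trigger is not applied may have left before the 2-hour point. The missing readings cannot be taken later.

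**Working it through.** No power, alpha or sample size figure is involved. The check sets the two rules side by side and follows each to the action it requires.

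**Inputs.** Section 6.3 thresholds: more than 15 mmHg for blood pressure and more than 20 bpm for heart rate, each confirmed by a repeat. Footnote 2: a rise judged significant by the Investigator. Section 6.3 adverse event rule: the change persists at all three post-dose time points.

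**Step 1: trigger conditions.** Section 6.3: {blood pressure, heart rate} × {rise, fall} = 2 × 2 = 4. Footnote 2: {blood pressure, heart rate} × {rise} = 2 × 1 = 2, each subject to judgement. The footnote reaches 2 of the 4.

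**Step 2: what each rule asks for at 2 and 3 hours.**

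| Finding at 1 hour | Section 6.3 | Footnote 2 |
|---|---|---|
| Confirmed fall above threshold | Required | Not called for |
| Confirmed rise above threshold, judged not significant | Required | Not called for |
| Confirmed rise above threshold, judged significant | Required | Called for |
| Rise at or below threshold, judged significant | Not required | Called for |
| Change meeting neither rule | Not required | Not called for |

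The rules disagree in rows 1, 2 and 4. In rows 1 and 2 the footnote loses readings that Section 6.3 demands.

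**Step 3: an illustrative case.** Section 6.3 does not name systolic or diastolic pressure; the example uses systolic. Predose 110 mmHg, 92 mmHg at 1 hour, confirmed on repeat.

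- Change: 92 − 110 = −18 mmHg, and 18 > 15, so the Section 6.3 trigger is met.
- Further readings required: 2 under Section 6.3, 0 under footnote 2.
- Time points available to the adverse event rule under footnote 2: 1 of 3. The rule cannot be applied.

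**Step 4: the other sections.** Sections 6.1.2 and 7.2.5 both point to Section 6.3, so the footnote is the outlier. Section 6.1.2 has a looser fault of its own. It uses the 1-hour change being clinically significant as the trigger, while Section 6.3 gives that status only after the 2 h and 3 h readings. Its sensible reading is the repeat-confirmed threshold.

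**Reach.** The footnote applies to all of about 415 subjects at about 130 sites. That is the population under the rule, not the number harmed by it.

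**The case against.** The strongest reply is that the body of the protocol already gets this right. Section 6.1.1 describes the Schedule as a summary and places the procedural detail in the sections that follow. Sections 6.1.2, 6.3 and 7.2.5 agree with one another. Footnote 2 does not forbid extra readings after a fall, so a site following Section 6.3 breaches nothing. The conditional readings are not a named endpoint, vital signs are analysed descriptively, and they are measured again at later clinic visits. Section 6.3 also has a general backstop: "Any post treatment clinically significant changes in vital signs (including weight) shall be noted by the Investigator and reported as an AE". The contrast between should in the footnote and must in Section 6.3 proves little, since Section 6.1.2 also says should. Finally, the worked example assumes a confirming repeat, which the footnote does not contain.

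Much of this stands, and it limits the consequence: one route to classifying an adverse event is at risk, not the vital-sign endpoint as a whole. It does not remove the conflict. A summary may leave out detail, but it should not narrow the direction of a safety trigger or change who decides, and the protocol text supplied does not say which statement prevails. The backstop rests on judgement in exactly the cases the numeric rule was written to settle, and it does not produce the missing readings. Later visits have no scheduled post-dose measurements. As to the repeat, a site using the footnote alone has no prompt to take one after a fall, although Section 6.1.1 allows it. Without it, the Section 6.3 trigger might not be assessed at all.

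**Conclusion.** The concern holds, with high confidence in the conflict between the texts. Footnote 2 is wrong as written: it covers 2 of the 4 conditions in Section 6.3, makes those two discretionary, and can leave 1 of the 3 time points the adverse event rule needs. It should be corrected, but it does not undermine the study.

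Two assumptions matter. First, change in Section 6.3 is taken to include falls. The section does not say so outright, but that is the ordinary meaning, nothing restricts it to rises, and Section 6.1.2 uses the same word. If only rises were meant, the conflict over judgement and thresholds would remain. Second, harm arises only where a site works from the footnote and not from Section 6. The documents give neither the frequency of that nor the variability of the 1-hour change, so no number of affected children is claimed.

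**What to change.** Replace the trigger in both footnote 2 and Section 6.1.2 with the Section 6.3 rule, for example:

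> When blood pressure at 1 hour differs from predose by more than 15 mmHg, or heart rate by more than 20 bpm, upward or downward, and a repeat reading bears this out, readings at 2 and 3 hours must be taken (see Section 6.3).

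Keep the term clinically significant for a change that persists at all three post-dose readings and is reported as an adverse event. This also repairs the loose cross-reference in Section 6.1.2. The thresholds are the sponsor's own; the only addition is to spell out both directions.

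The cost is two wording edits and a memo to sites. A few more children may stay for the later readings, which Section 6.3 already requires.
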